The present proposal is designed to investigate the mechanisms of the synergistic effect(s) of low dose CNI and mTOR inhibitors (Everolimus) in controlling alloreactive T and B cells while expanding Tregs.

Our hypothesis, based on published data and our laboratory results (see preliminary data-Supportive documents), is that mTOR inhibitors allow expansion of Tregs and that low exposure to CNI is sufficient to control alloreactive T cells. Decreased exposure to CNI and concomitant increase of Tregs will then translate to improved renal allograft function and histology.

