### **Objectives**

The overall aim of the present study is to prospectively investigate the impact of two maintenance immunosuppressive regimens (both prednisone-free) on subpopulations of T and B cells and on renal allograft function at 12, 24 and 36 months post-randomization. One regimen combines low CNI exposure (tacrolimus) with concentration controlled Everolimus, and the second combines standard dose CNI (Tacrolimus) with MMF.

The primary endpoints of the study are to: 1) evaluate the impact of the two maintenance immunosuppressive regimens on T cells subpopulations, including regulatory T cells and B cell subpopulations, at different time points post renal transplant, and 2) determine the impact of the two regimens on renal allograft function at 12, 24 and 36 months post-randomization (post-transplant). Secondary endpoints of the study are to: 1) evaluate the impact of the two regimens on allograft immunohistopathology gene expression profiles and graft infiltrating cells (memory T cell (CD4+ or CD8+ CD45RO+), TREG (CD4+FoxP3+), memory B cell (CD19+CD27+)) at 12 and 24 months in renal allograft biopsies, and 2) evaluate the impact of the regimens on acute rejection, graft loss and death at 12, 24 and 36 months post-transplant.

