Kidney biopsy samples will be collected with standard-of-care samples at time of transplant (back table), 3 months, 12 months and at 24 months post-transplant. These will help evaluateand compare the impacts of the two maintenance immunonousuppressive regimens on allograft immunohistopathology. Gene expression profiles will also be analyzed. These samples will be processed in the principal investigator's research laboratory.

Both groups of subjects will be followed through 36-months post-randomization. In addition to monitoring renal allograft function, we will evaluate the incidence of acute rejection, subject and graft survival, incidence of hypertension (HTN), malignancies, opportunistic infections and post-transplant diabetes mellitus (DM).

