**Statistical analysis:**

The primary endpoints of the study are graft function and subpopulations of T cells, including regulatory T cells and B cell subpopulations at 3, 6, 12, 24 and 36 months post kidney transplant. The secondary endpoints of the study include 1) incidence of acute rejection, graft loss, and death at 12, 24 and 36 months post kidney transplant; 2) allograft immunohistopathology and gene expression profiles at 12 and 24 months post kidney transplant.

We will run univariate and bivariate analyses for all variables prior to our main analyses. We will evaluate continuous variables using t-tests or F-tests and categorical variables using  $\chi^2$ . We will examine data distributions and test all variables for linear relationships or non-linear relationships.

Descriptive statistics (means, standard deviation, frequency) and correlations (both Pearson and Spearman) among variables will be calculated for preliminary data assessment.

Necessary transformation and imputations will be carried out based on the raw data distribution.

As missing data are inevitable in a longitudinal study, we will determine whether missing data are MCAR (data are missing completely at random), MAR (data are missing at random), or NMAR (not missing at random). If missing data are MCAR or MAR, it is likely that the standard multivariate computations using PROC MI (multiple imputations) will not result in biased standard error estimates. However, if missing data are NMAR, we will use the "pattern mixture" approach to compute a weighted average of the parameters that are associated with the missing data to estimate what the data would have been.

For the primary objective, we hypothesize that subjects receiving low dose CNI with mTOR inhibitor (Everolimus) will exhibit significantly greater graft function and higher numbers of regulatory T cells as compared to the standard dose CNI+MMF group.

We will utilize both repeated-measures ANOVA and random mixed effect models to compare the trajectory change in graft function and proportion of regulatory T cells over 12, 24 and 36 months between the two experimental groups. The method of estimation will be maximum likelihood (ML).

---

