A variety of covariance structures (first order regressive, compound symmetry, Toeplitz, variance components, unstructured) will be carefully examined and compared using the best fitting statistics, such as Akaike's Information (AIC) and Bayesian Information Criteria (BIC). These statistics are likelihood functions and can be compared across models. If, in spite of randomization, distributions of subjects' baseline characteristics are found to be different between the two experimental groups, these variables will be entered as covariates in the statistical analysis.

For the secondary endpoints, we will use logistic regression, Kaplan-Meier method, and Cox proportional hazards models to analyze time-to-event outcomes (acute rejection, graft failure, and death). For allograft immunohistopathology and gene expression profile outcomes, we will first develop a comprehensive immune profile of each participant by longitudinal analysis of frequency and function of T and B cell subsets. We will examine how these correlate with immunohistopathology and alloantibody production using Pearson or Spearman correlations. We will compare correlation coefficients between the two experimental groups using Z -tests to determine the distinct effects of each treatment arm. We will also compare the trajectory changes in cell populations and antibody production over 12, 24 and 36 months using both repeated measures ANOVA and random mixed effect models. All tests will be two-sided, and an error rate of  $\alpha < 0.05$  will be considered statistically significant. All data analyses will be performed using SAS 9.2 statistical software (SAS Inc., Cary, NC).

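### The only between-arm analysis tied to biopsy histology tests whether a correlation differs by arm, not whether histology differs; gene expression has no between-arm analysis of its own

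*Combined protocol and SAP*

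**What the plan says.** The aim is stated as an effect of treatment on the graft. The Objectives section lists as a secondary endpoint to "evaluate the impact of the two regimens on allograft immunohistopathology gene expression profiles and graft infiltrating cells" at 12 and 24 months. The biopsy paragraph of the study design says the samples will help "compare the impacts of the two maintenance immunonousuppressive regimens on allograft immunohistopathology", and adds "Gene expression profiles will also be analyzed" without naming a method. The rationale predicts a direction: "Decreased exposure to CNI and concomitant increase of Tregs will then translate to improved renal allograft function and histology". The Statistical analysis section repeats the secondary endpoint as "allograft immunohistopathology and gene expression profiles at 12 and 24 months post kidney transplant".

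For these outcomes the Statistical analysis section sets out three steps:

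1. Build an immune profile of each participant from T and B cell subsets.
2. Correlate that profile with histology and alloantibody production, by Pearson or Spearman.
3. "We will compare correlation coefficients between the two experimental groups using Z -tests to determine the distinct effects of each treatment arm".

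The same paragraph then gives repeated-measures ANOVA and mixed models for cell populations and antibody production to month 36. Earlier in the section, univariate and bivariate analyses are promised for all variables ahead of the main analyses, with t-tests or F-tests for continuous variables and chi-square for categorical ones.

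Biopsies are scheduled at "time of transplant (back table), 3 months, 12 months and at 24 months post-transplant". The study title, however, refers to gene expression in biopsies at 12, 24 and 36 months.

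**The concern.** The objective and the test answer different questions. Whether a regimen improves histology is a question about the level of histology in each arm. Whether the correlation between immune profile and histology differs by arm is a question about association. Either can be true without the other.

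The wording of the plan invites the two to be confused, because it presents the comparison of correlations as the way to establish what each arm does. A difference in correlation could then be reported as a treatment effect on the graft, while the histology difference itself has no planned main estimate or interval. A real histology difference could also go unreported if only the stated test were run.

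For gene expression the gap is wider. It is named at the head of the paragraph, but none of the steps that follow uses it, so the comparison and the genes could be chosen after the data are seen.

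**Working it through.** **Inputs from the plan.** 20 per arm, 1:1 allocation, two-sided 0.05, 10% attrition at month 12, so 20 × 0.9 = 18 per arm. The plan gives no evaluable number for month 24. All shifts, correlations and cut-points below are assumptions.

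**The plan's own figure first.** The sample size section states power of 0.82 and 0.99 for effect sizes of 1.0 and 2.0 on the two primary endpoints. A two-sample t-test with 18 per arm gives 0.830 and 0.9999, so the first figure reproduces and the second is met. This shows that the plan already reasons in terms of a direct comparison of arms for its primary endpoints. The point here does not rest on those figures.

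**What the Z-test measures.** With n per arm,

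z = [atanh(r₁) − atanh(r₂)] / √(2/(n−3)).

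At n = 18 the standard error is √(2/15) = 0.365. Only the two within-arm correlations enter. For a continuous measure, adding a constant to every histology value in one arm leaves that arm's correlation unchanged, so z is unchanged. This is algebra and needs no assumed value.

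**Illustration, continuous measure.** Bivariate normal data, correlation 0.5 in both arms, 18 per arm, 20,000 simulated trials per row:

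| True histology shift (SD) | Z-test rejects | t-test rejects |
|---|---|---|
| 0 | 5.0% | 5.1% |
| 0.5 | 4.6% | 31% |
| 1.0 | 4.7% | 83% |
| 1.5 | 4.7% | 99% |
| 2.0 | 5.0% | 100% |

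With 14 per arm (assumed, for later loss of biopsies) and a 1 SD shift, the figures are 5.0% and 72%.

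**Reverse case.** No histology shift, 18 per arm. Correlations of 0.6 and −0.3 give Z-test rejection of 81% and t-test rejection of 5%; the milder 0.6 and 0 give 49% and 5%. The Z-test can therefore be significant when histology does not differ at all.

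**Bounded ordinal scores.** Here the invariance is not exact. I took a four-level score (latent normal cut at −0.5, 0.5 and 1.5) with 18 per arm. With latent correlation 0.5, a shift of −1 SD pushes scores to the floor and lowers the mean Spearman correlation in that arm from 0.44 to 0.38; Z-test rejection stays near 6%. With latent correlation 0.8 and a shift of −1.5 SD, Z-test rejection is about 16% among trials where it can be computed. A shift of +1 SD leaves the correlation alone only because these cut-points then produce a mirror-image distribution. Where the Z-test does respond, it responds to floor or ceiling compression, and the result is still not an estimate of the histology difference.

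**Precision of a direct comparison.** The 95% half-width for a mean difference is t(0.975, 2n−2) × √(2/n) SD. At n = 18 this is 2.032 × 0.333 = 0.68 SD; at n = 14 it is 0.78 SD.

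**The case against.** The strongest reply is that a direct comparison is already planned. The general tests cover all variables, arm is the natural grouping in a two-arm randomised trial, and the phrase placing work ahead of the main analyses sits in the sentence before the one that names the tests. This stands in part. A reader might infer that the plan contains no comparison of biopsy variables between arms at all, and the documents do not support that. What they offer is a generic, under-specified comparison: no arm contrast, biopsy endpoint, time point, estimate or interval is named.

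Second, the trajectory models might cover graft-infiltrating cells, since the Objectives section defines these as memory T, regulatory T and memory B cells, and the models are for cell populations. A reader might infer from the biopsy schedule, which ends at month 24, that the models to month 36 must concern blood only. The documents do not settle this: the title names biopsies at 36 months. Coverage is unclear, and the two passages need reconciling. In any case the models name neither histology nor gene expression.

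Third, a reader might infer that the Z-test holds its 5% rejection rate whatever the histology shift. As shown above, that is true for a continuous measure but not in general for bounded scores.

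Fourth, the study has a mechanistic purpose and is a pilot that disclaims power for secondary outcomes. The correlation analysis does serve that purpose and should be kept. Low power is not the complaint, and the disclaimer does not supply the missing estimate.

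**Conclusion.** The concern holds in this form. The only analysis specific to histology that compares the arms is aimed at a different quantity from the stated objective, and gene expression has no between-arm analysis specific to it. The mismatch follows from the text and from the definition of a correlation; the rejection rates of about 5% against 83% are an illustration under assumed settings, not a measure of risk in this trial. It should be corrected, but it is confined to secondary endpoints. A reader might infer that it weakens the primary findings on graft function and blood cell subsets. It does not: those have their own between-arm models.

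**What to change.** In the Statistical analysis section:

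- Make the main analysis of histology, graft-infiltrating cells and gene expression at months 12 and 24 a direct between-arm comparison, reporting an estimate with a 95% confidence interval. For ordinal scores use a rank-based method, for example the probability that a score in one arm exceeds a score in the other, with ties counted half.
- Name the histology score and the gene set before the data are seen, with false discovery rate control if many genes are tested.
- Keep the Z-test on correlations as an exploratory mechanistic analysis, and delete the clause that presents it as determining the effects of each arm.
- Reconcile the title's 36-month biopsies with the schedule that ends at month 24, and say whether the trajectory models include graft-infiltrating cells.

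The cost is plan wording and a little more analysis on biopsies already scheduled. The intervals will be wide (half-width about 0.68 SD at 18 per arm), and false discovery control will mean fewer genes declared significant.

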### **Sample size and power**

[figure not shown]
We calculated our sample power for the two primary endpoints based on our clinical experience and small pilot data. Using a two-tailed  $\alpha$  of 0.05, the anticipated effect sizes corresponding to each specific aim between the two treatment arms were calculated using a minimum of 80% statistical power and assumed 10% attrition at 12 months.

For the sample size of  $n= 20$  in each group, the proposed study will have a power of 0.82 and 0.99 to detect effect size of 1.0 and 2.0 for graft function and % regulatory T cell change, respectively, between the two treatment arms. Because this is a pilot study, we do not consider the statistical power of secondary outcomes; It is anticipated that a much larger sample size will be needed in order to achieve statistical power for the secondary endpoints in this proposed study.

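### The between-arm Z-tests on correlations form an unlisted, unadjusted family at two-sided 0.05, yet a significant result is to be read as a distinct effect of an arm

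*Combined protocol and SAP*

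**What the plan says.** The Statistical analysis section first builds an immune profile of each participant by "longitudinal analysis of frequency and function of T and B cell subsets". It then says: "We will examine how these correlate with immunohistopathology and alloantibody production using Pearson or Spearman correlations". The next sentence sets the comparison between arms: "We will compare correlation coefficients between the two experimental groups using Z -tests to determine the distinct effects of each treatment arm". The threshold is general: "All tests will be two-sided, and an error rate of" below 0.05 counts as significant.

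The tissue outcomes are secondary endpoints, named as "allograft immunohistopathology and gene expression profiles at 12 and 24 months post kidney transplant". The Study design section has biopsies taken "at time of transplant (back table), 3 months, 12 months and at 24 months post-transplant", so more visits than the two endpoint visits could enter the correlations.

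No section lists the cell subsets, histology scores, antibody measures or visits to be paired for the Z-tests. None names a lead pair, sets an adjustment or calls these tests exploratory. The Sample size and power section adds: "Because this is a pilot study, we do not consider the statistical power of secondary outcomes". It says nothing there about false positives.

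**The concern.** The list of comparisons is open, each is tested at 0.05, and significance is given a causal-sounding reading. The more pairs are examined, the more probable it is that at least one between-arm difference in correlation arises by chance. As written, that one result could be reported as a mechanism specific to low-dose tacrolimus plus everolimus. The study rationale says the trial is meant to investigate mechanism, so a chance finding here bears on the interpretation the investigators care about, even though it is secondary.

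The open choice between Pearson and Spearman adds a smaller freedom. Reporting whichever coefficient is significant raised the error of a single null test from 5.2% to 6.9% in simulation.

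**Working it through.** **The plan's own figure.** The plan gives no error rate or power for these Z-tests. Its only power figures are 0.82 and 0.99 for the primary endpoints at effect sizes 1.0 and 2.0. A two-sided t-test at 0.05 with 18 per arm (20 less 10% attrition) gives 0.83 and 0.9999. The stated figures are therefore reproduced to within about one point, which supports working with 18 to 20 per arm.

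**Number of tests, k (assumed).** The Objectives section names four graft-infiltrating subsets: memory CD4, memory CD8, Treg and memory B. Using them for the immune profile is my assumption. I take one histology score and one antibody measure as two outcomes, and months 12 and 24 as two visits.
- One subset: 1 × 2 × 2 = 4 tests.
- Four subsets: 4 × 2 × 2 = 16 tests.
- Four subsets with frequency and function counted separately: 4 × 2 × 2 × 2 = 32 tests.

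**Independent tests.** P(at least one false positive) = 1 − 0.95^k.
- k = 4: 0.186
- k = 16: 0.560, with 16 × 0.05 = 0.8 false positives expected
- k = 32: 0.806, with 32 × 0.05 = 1.6 expected
- The chance passes one half between k = 13 (0.487) and k = 14 (0.512).

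**Correlated tests.** Measures from the same patients are not independent, so the family was simulated. Settings: 20 per arm, normal data, no true difference between arms, and a common correlation from 0 to 0.8 among subsets, among outcomes and between visits. The test statistic is the difference in Fisher z divided by √(2/(n − 3)) and compared with 1.96. The single-test error stayed near 0.05, so the excess comes from the number of tests.

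| Tests | Chance of at least one false positive |
|---|---|
| 4 | 0.15 to 0.18 |
| 16 | 0.29 to 0.57 |
| 32 | 0.39 to 0.80 |

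The low end of each range belongs to strong correlation and the high end to independence. Repeat runs differed by about 0.01. With 18 per arm and moderate to strong correlation (0.3 to 0.7 between measures, 0.5 to 0.7 between visits), the results were 0.36 to 0.53 for 16 tests and 0.53 to 0.76 for 32.

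**What one test can detect.** With 20 per arm the standard error is √(2/17) = 0.343, so significance needs a Fisher z difference of 1.96 × 0.343 = 0.67, for example an observed r of 0 against 0.59. Power for true correlations of 0.5 and 0 is about 0.36, or 0.32 with 18 per arm. A significant result therefore carries little evidential weight when many pairs have been tried.

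**After adjustment.** Benjamini-Hochberg at 5% over the full list brought the chance of any false claim, with no true differences, down to 0.03 to 0.06.

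**The case against.** The best defence is that this is a pilot. The Sample size and power section sets secondary power aside and expects that a much larger study would be needed. The correlations themselves are introduced in the language of examination. The primary comparisons of graft function and regulatory T cells, and the direct comparison of cell and antibody trajectories between arms, do not depend on the Z-tests. All of that stands, and it limits the consequence. It does not remove the point: a statement about power is not a statement about false positives, and nothing withdraws the stated purpose of the Z-tests.

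A reader might also infer two stronger claims.

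*That a false claim is more likely than not.* The documents do not support this. It depends on a test count they do not give; 16 strongly correlated tests stay well below one half, and so do 32 at the strongest correlation considered. Nor does the plan say that every possible pair will be tested.

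*That the Z-test is the wrong statistic, because everolimus may widen the spread of Tregs.* With equal slopes and a marker standard deviation 1.5, 2 or 3 times larger in one arm, the Z-test rejects in 9%, 22% and 56% of simulated trials, while an arm-by-marker slope interaction stays at 5%. But the true correlations do differ in that setting, so these rejections are not false positives for the hypothesis tested. When the correlation is the same and one arm's marker is simply rescaled by those factors, the Z-test stays at 5% and the slope interaction rejects in 9%, 15% and 26%. Which test misleads depends on the scale of the marker. The protocol hypothesises more Tregs, not more variable ones, and already allows transformation.

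**Conclusion.** The concern holds as a multiplicity and interpretation problem. The family is unlisted, each test is at two-sided 0.05, and significance is tied to a claim about the arm. Even 4 tests take the chance of a false claim to about three times the nominal 5% or more (0.15 / 0.05 = 3). At 16 or 32 tests it is roughly six to sixteen times (0.29 / 0.05 = 5.8; 0.80 / 0.05 = 16). These figures rest on 20 per arm, normal data, no true difference and an assumed number of tests. That the error is well above 5% does not depend on the exact count; whether it exceeds one half does. The finding does not extend to the primary analysis, and it gives no ground for requiring a different test statistic.

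**What to change.** In the Statistical analysis section, before any data are analysed:

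1. List the cell measure and outcome pairs, the visits, and one coefficient (Pearson or Spearman) for each pair.
2. Apply Benjamini-Hochberg control of the false discovery rate at 5% across that whole list, and report how many pairs were tested. This limits the expected share of false claims among those made.
3. Report each between-arm difference in correlation with its 95% confidence interval, whether significant or not.
4. Replace the closing purpose clause of the Z-test sentence with: to explore whether the association differs between arms.

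The Z-test itself can stay. The cost is a short list and a few lines of analysis code, with no extra patients or samples. The downside is that fewer secondary correlations will be called significant, in a study that already has little power to detect them.

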**Twenty (20) subjects will begin low dose tacrolimus with concentration controlled everolimus (treatment arm)**

Tacrolimus will be initiated according to our practice. In this treatment arm, the Tacrolimus dose will be adjusted from day 3 on, to a target whole blood trough concentration of 4 ng/mL to 7 ng/mL. From month 2 until Month 6, the target Tacrolimus trough level will be 3 ng/mL to 6 ng/mL. After month 6, the Tacrolimus dose should be adjusted in order to achieve a target trough level of 2 ng/mL to 5 ng/mL.

From day 5 on, the starting dose of Everolimus (0.75 mg bid) will be increased if the trough level is < 3 ng/mL, or reduced if the trough level is > 8 ng/mL.

All drugs will be administered in an open label fashion.

The following transplant recipient data will be collected at the time of randomization:.  
Demographics: Age at transplantation, sex and race.

Causes of end-stage renal disease

Transplant related information: donor age, histocompatibility and cross match data, viral serology, history of acute rejection and delayed graft function, use of ACEI and/or ARB, level of renal allograft function - estimated GFR ( e-GFR(12) using MDRD formula, proteinuria.

Blood samples will be obtained prior to randomization from all renal transplant recipients for baseline T and B cell functional activity and characterization of the cell subpopulations by flow cytometry.

-All recipients will be routinely followed at our Transplant center with post-transplant labs (SMA7, CBC, and relevant immunosuppression trough levels).

Additional blood will be collected and analyzed for the study at 3, 6, 12, 24 and 36 months post-randomization. If the final blood sample cannot be drawn at the 36 month timepoint, it may be drawn up to 50 months post-transplant. These samples will be used to investigate the impact of the two maintenance immunosuppressive regimens on subpopulation of T cells in comparison with baseline levels. Specifically,

---

we will look at regulatory T cells (Treg: Foxp3+CD4+ CD25bright+) that could have been generated via the two maintenance immunonousuppressive regimens, and correlate the generation of with their function.

RNA from peripheral blood will be also collected and stored for post-hoc analyses of T and B-cell immunoresponse gene expression via gene arrays.

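### The only significance rule that reaches the biopsy gene-expression endpoint is 0.05 for every test, with no gene-level test, gene family or multiplicity control specified

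*Combined protocol and SAP*

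**What the plan says.** The Objectives section lists as a secondary endpoint to "evaluate the impact of the two regimens on allograft immunohistopathology gene expression profiles and graft infiltrating cells". The Statistical analysis section repeats it as "allograft immunohistopathology and gene expression profiles at 12 and 24 months post kidney transplant". The Study design section confirms that biopsy expression profiles will be analysed, without naming a platform or the number of genes.

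On method, the Statistical analysis section begins: "For allograft immunohistopathology and gene expression profile outcomes, we will first develop a comprehensive immune profile of each participant". What follows concerns T and B cell subsets, their correlation with histopathology and alloantibody, and a between-arm comparison: "We will compare correlation coefficients between the two experimental groups using Z -tests". The longitudinal models at the end of that paragraph are for cell populations and antibody. No gene-level comparison appears. Earlier in the section, t-tests or F-tests are the general default for continuous variables, to be run ahead of the main analyses.

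The same paragraph then closes with one rule for everything: "All tests will be two-sided, and an error rate of" alpha below 0.05 "will be considered statistically significant. All data analyses will be performed using SAS 9.2 statistical software". It makes no exception. The plan contains no family-wise or false-discovery-rate procedure and no pre-named gene list. It does not label biopsy expression as exploratory.

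Blood RNA is treated separately. It is stored for "post-hoc analyses of T and B-cell immunoresponse gene expression via gene arrays".

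**The concern.** Expression profiling usually means many comparisons at once. A threshold of 0.05 per comparison limits the error of each test, but not the number or share of false calls in the resulting gene list. An analyst who follows the plan as written has the t-test or F-test default and the 0.05 rule, and nothing else. That could produce a list of genes reported as significantly different between regimens of which a large and unknown part is chance.

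What is at stake is how a named secondary endpoint, which also appears in the study title, is interpreted. Graft function and regulatory T cells, the primary endpoints, are not touched.

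**Working it through.** **Inputs from the plan.** Alpha 0.05, two-sided, for all tests (Statistical analysis). 20 per arm, 10% attrition at 12 months, power 0.82 at effect size 1.0 and 0.99 at effect size 2.0 (Sample size and power). After attrition, 20 × 0.90 = 18 per arm.

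**Inputs assumed.** The number of genes *m* and the share *π* of genes that truly differ between arms are not in the documents. The ranges used are *m* = 50 to 20,000 and *π* = 1% to 30%. The true standardised difference *d* for an affected gene is also assumed. The main case uses 1.0, borrowed from the plan's effect size for graft function.

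**Step 1: the plan's own power figures.** A two-sample t-test (noncentral t) with 18 per arm gives 0.830 at *d* = 1.0 and 0.9999 at *d* = 2.0, close to the stated 0.82 and 0.99. With 20 per arm the first figure would be 0.869, so the stated power fits the sample after attrition. The 0.830 is used below as per-gene power.

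**Step 2: count of false calls if no gene differs.** Expected false positives = 0.05 × *m*:

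- 100 genes: 5
- 500 genes: 25
- 1,000 genes: 50
- 20,000 genes: 1,000

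The chance of at least one false call is 1 − 0.95^50 = 0.92 for 50 genes and 0.994 for 100 genes. Both assume independent tests, which co-expressed genes would not satisfy. The expected counts do not need independence.

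**Step 3: share of calls that are false.** Step 2 cannot give a share, because with no true effects every call is false by definition. In general:

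false share = 0.05(1 − *π*) / [0.05(1 − *π*) + power × *π*]

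With power 0.83:

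| Share truly different | Calculation | False share |
|---|---|---|
| 1% | 0.0495 / (0.0495 + 0.0083) | 86% |
| 2% | 0.0490 / (0.0490 + 0.0166) | 75% |
| 5% | 0.0475 / (0.0475 + 0.0415) | 53% |
| 10% | 0.0450 / (0.0450 + 0.0830) | 35% |
| 20% | 0.0400 / (0.0400 + 0.1660) | 19% |
| 30% | 0.0350 / (0.0350 + 0.2490) | 12% |

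The number of genes cancels out. With 1,000 genes, for example, one expects 49.5 false and 8.3 true calls at 1%, and 45 false and 83 true calls at 10%.

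**Step 4: where false calls become the majority.** Setting the share to one half gives *π* = 0.05 / (0.05 + power). At *d* = 1.0 this is 0.05 / 0.88 = 5.7%. It is 14.0% at *d* = 0.5 (power 0.308), 7.2% at *d* = 0.8 (power 0.645) and 4.8% at *d* = 2.0.

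**Step 5: what a 5% false discovery rate would cost.** Replace 0.05 in step 3 by a per-gene threshold *a*, recompute power at *a* (18 per arm, *d* = 1.0), and solve for a false share of 0.05:

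| Share truly different | Per-gene threshold | Per-gene power |
|---|---|---|
| 1% | about 0.00004 | about 7% |
| 5% | about 0.0007 | about 27% |
| 10% | about 0.0024 | about 40% |

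**The case against.** The strongest reply is that the plan nowhere says genes will be tested one at a time. The paragraph that names gene expression goes on to describe cell-subset profiles and correlations, and gene expression then drops out of it. The alpha sentence sets a level without saying that p-values are unadjusted, so false-discovery-adjusted p-values judged at 0.05 would not contradict it. This stands as a description. A reader might infer that unadjusted gene-by-gene testing is a stated rule, and the documents do not support that. The rule reaches genes only because it covers all tests. What remains is that the plan offers no other rule and mentions no adjustment.

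A second reply is that arrays are named only for stored blood RNA, which is already called post hoc. This also stands. The biopsy platform is not given, and a small targeted panel is as consistent with the text as a genome-wide array. The point therefore rests on the biopsy endpoint, and every gene count here is an assumption.

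Third, a reader might infer that most significant genes will be false, or that gene expression carries the trial's mechanistic conclusion. Neither is supported. The first depends on an unknown share of true differences. On the second, the hypothesis in the rationale and the primary objective is framed around regulatory T cells, control of alloreactive cells and graft function.

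Finally, the study calls itself a pilot and expects that secondary endpoints would need a much larger sample. That remark explains only why power for secondary outcomes was not considered. It does not stop those outcomes being declared significant at 0.05, and lower power raises the false share.

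**Conclusion.** The concern holds in a limited form. A named secondary endpoint has no specified gene-level test, gene family or multiplicity handling, and the one rule that covers it would leave false gene calls uncontrolled if applied gene by gene. About 5% of unaffected genes would be called significant whatever the platform. Whether false calls outnumber true ones cannot be settled from the documents. At 18 per arm the crossing point lies between about 5% and 14% of genes truly different, for true differences from 2.0 down to 0.5. The share calculation treats all affected genes as having the same effect size and uses the 12-month attrition figure for both visits. The gap should be closed before expression data are analysed, but it bears on how gene findings are read and not on the primary results.

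**What to change.** In the Statistical analysis section, except gene expression from the general 0.05 rule and add a short statement that:

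- names the between-arm gene-level test and the gene family (platform and number of genes, or a pre-named panel);
- declares genes by Benjamini-Hochberg false discovery rate at 5% or 10% within each tissue and visit, or else applies Holm to a short pre-named set;
- labels all other gene results hypothesis-generating, including the blood arrays already described as post hoc.

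The false-discovery rule cannot operate until the test and family are defined, so this takes more than a single sentence. It needs no extra patients, samples or visits. The price is fewer genes called significant and low power for each gene: about 7% to 40% at a 5% false discovery rate if 1% to 10% of genes differ by 1.0 standard deviation. A short pre-named set is the way to limit that loss.
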